# The Psychosocial Effects of Systemic / Family Constellation: An Observational Follow-up Study

## I. STUDY PROTOCOL

## Background and aims

Family / systemic constellation therapy is a short-term group psychotherapy aiming to help clients better understand and resolve their conflicts within their personal systems, which in turn might lead to a decrease in psychopathological or functional somatic symptoms (Hellinger, 2003). The personal system addressed is most often the family but other inter- or intrapersonal systems (e.g., ego parts, victim-perpetrator dyads) can also be the target of the intervention. This therapeutic modality was developed in Germany in the early '90s integrating elements of – among others – psychodrama, family sculptures, contextual therapy, and certain South-African aboriginal traditions (Butollo et al., 2017) and has become particularly popular in Europe and South America and even became part of the public health care system in certain countries. Compared to its use by thousands of therapists of various theoretical and professional backgrounds all over the world, little effort has been made to generate empirical data regarding the effectiveness and safety of this intervention.

We believe that the large discrepancy between the relatively high level of penetration into the practice of complementary and alternative medicine versus the low quantity of evidence on effectiveness stems largely from academic psychology's reluctance to engage with at least two metaphysical / anthropological postulates of family constellation therapy. Firstly, the theory of family constellation therapy assumes that an individual's mental and physical health might be significantly influenced by major life events of other members of the personal system even if they lived generations before (e.g., the death of a mother during childbirth might have an effect on her descendants' anxiety level and reproductive success for several generations even if the original event has never been talked about in the descendant's life). While – due to recent developments in epigenetics and the better understanding of transgenerational trauma (Kellermann, 2013) – this and similar concepts are less shocking to the academic community than they were 3-4 decades ago when family constellation therapy was developed, they are still in sharp contradiction with the common understanding that the etiological factors of any physical or mental illness are to be sought in bio-psycho-social events, situations, or conditions occurring or existing around and after the individual's conception.

The second distinctive feature is that the theory of family constellation therapy assumes that the life-altering, relevant pieces of information are 'stored' and somehow can be 'downloaded' not just automatically and unconsciously by the members of the same system but intentionally by outsiders as well (Preiss, 2015). This accessibility of system-relevant information makes it possible that participants of the single-occasion intervention (who are unknown to each other) are able to perceive and verbalize thoughts, physical perceptions, emotions associated with the history of the system, often unknown even to the recipient of the given constellation. This somewhat 'mystical' re-presentation of unknown facts and hidden dynamics makes it possible for the recipient of the constellation to better understand the etiology of their mental or physical symptoms and intentionally change these very same dynamics. How this storage and access of system-relevant information occurs is highly debated and uncertain; the most-widely held

explanation of these processes use the morphic / morphogenic field and -resonance concepts (cf. storage) of the biologist Rupert Sheldrake (Sheldrake, 2011) in combination with the function of mirror neurons (cf. way of accessing stored information by non-members of the system) (Lahore, 2009).

Regardless of whether we fully understand the exact mechanisms of action of a therapeutic modality and if its certain assumptions fit the contemporary paradigms of health sciences, we argue that collecting empirical data on an intervention's effectiveness and safety is a public health necessity, especially if it is so widely used as family constellation therapy is (and it certainly could provide further impetus to the study of the mechanisms of action and the potential reconsideration of the accuracy of our paradigms).

The very limited number of previous prospective, peer-reviewed studies into family constellation therapy's therapeutic effectiveness reported that the intervention was effective in reducing general, non-diagnosis-specific psychopathology and psychological distress (Hunger et al., 2015; Krüger & Schmidt-Michel, 2003; Weinhold et al., 2013) as well as improving quality of life and functioning in interpersonal relationships (Hunger et al., 2014; Hunger et al., 2015).

The aim of the present study was to collect and analyze further data from the real life setting on family constellation therapy's effectiveness in improving mental health and its tolerability 1) using a mid-term time frame (≥6 months) to evaluate client outcomes, 2) employing active monitoring (not just passive surveillance) of potential iatrogenic effects, and 3) providing information on the presence or absence of therapist effects.

## Participants and procedure

Participants of the study will be recruited in Hungary from individuals in the general population who will express their intent to participate in a 2-day family constellation workshop on a fee-for-service basis (private setting) with one of the three professionals participating in the study. All three intervention providers will be highly trained in both general mental health care delivery (one therapist with a background in clinical psychology, while the other two will be trained in medicine) and family constellation therapy (10-20 years of experience). Participation in the study will be voluntary and will occur as a combination of online and paper-pencil data collection after participants give their informed, written consent. Neither the therapists nor the participants will receive financial compensation for their participation.

The assessment protocol will include a pre-intervention assessment, a follow-up approximately 4 weeks after the intervention (this time is estimated to be necessary for the single-occasion, 2-day workshop to have most of its effects; cf. the focus on changes in perceived quality of interpersonal relationships and related mental health symptoms), and finally, six months post-intervention. Significant efforts will be made (follow-up email and three attempted phone calls) to encourage participants to complete the questionnaires at both follow-up assessment points.

#### Intervention

The intervention will be administered in a group setting in which approximately 15-25 participants, unknown to each other, will meet for a one-time, 2-day, facilitator-led workshop. Each constellation will start with a brief interview between the facilitator and the active client to clarify the individual's goal with the intervention. This will be followed by a decision about which members/elements of the client's (inter)personal system will play a significant role in the issue presented, and these will be represented by other group members during the constellation.

The representatives (including the client's representative) will be positioned in the room by the client initially, with spatial distances, angles, and body postures meant to correspond to the client's inner image of the system ("problem constellation"). This will allow the facilitator to identify the dynamics beneath the client's presenting concern, while at the same time will help the client reflect on their internal experience from a more objective, partially external point of view (as they will be observers and not participants at this point). This part of the process will be largely non-verbal, focusing on what participants begin to experience as being part of the structure created by the active client (cf. Orban 2008).

Next, the representatives will be asked by the therapist about their physical sensations, feelings, and thoughts they will have while in their positions. Rearrangements, spatial adjustments, and brief, ritualized conversations will be made based on the principles of healthy functioning within a system until a constellation is identified that will offer a resolution or relief for the client (who at this point might become an active participant of the constellation if they feel ready to do so). Ideally, this "solution constellation" will provide a new, more adaptive framework for the client to feel, think, and behave in the given system (Hunger et al. 2015).

#### Measures

Ad hoc items to assess sociodemographic characteristics and iatrogenic effects

To assess sociodemographic characteristics, questions will be administered to assess participants' sex, age, relationship/marital status, and educational attainment. A couple of freetext questions will also be asked to participants to explore potential iatrogenic effects (T2 & T3, Did you experience any negative change in relation to your mental or physical health during or since the family constellation workshop?). If respondents answer affirmatively to the second question, it will also be asked if they believe the changes are associated with their participation in family constellation therapy (yes, no, or unsure).

Brief Symptom Inventory (BSI)

The Hungarian version (Urbán et al. 2014) of the BSI (Derogatis & Spencer 1993) will be used to measure an individual's overall psychopathology level. This tool consists of 53 items covering nine symptom dimensions: somatization, obsessive-compulsive symptoms, interpersonal sensitivity, depression, anxiety, hostility, phobic anxiety, paranoid ideation, and psychoticism. Out of the three global measures of pathology and distress, the General Severity Index (GSI, mean of all items) will be used in the present study.

Experience in Personal Social Systems Questionnaire (EXIS.pers)

The Hungarian version of the EXIS.pers (Hunger et al. 2017) will be used to assess the subjective experiences of the individual in their personal social system (e.g., family, circle of friends).

Patient Health Questionnaire-15 (PHQ-15)

The Hungarian version of the PHQ-15 (Kroenke et al. 2002) will be used to evaluate the intrusiveness of somatic symptoms and a tendency toward somatization. The assessment tool contains 15 items, each addressing a frequently occurring mild, physical symptom such as back pain or trouble sleeping.

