#### II. STATISTICAL ANALYSIS PLAN

All analyses will be carried out using SPSS for Windows. Baseline characteristics of study completers versus drop-outs will be compared using the Mann-Whitney U (age) and the chi-squared (categorical variables) test. Effect size will be expressed using effect size r (Mann-Whitney U test) and Cramer's V (Chi-squared test). Considering the likely non-normal distribution and occasionally ordinal nature (SCOFF) of the outcome variables, the effectiveness of the intervention will be investigated using Wilcoxon paired sample tests in the primary analyses. Separate comparisons will be made to explore potential changes from baseline to 4-week post-intervention as well as baseline to 6-month follow-up. Effect size r will be computed to express the magnitude of the changes.

Given that the normality assumption is relatively rarely examined and therefore parametric tests are used most often in effectiveness research, to facilitate inter-study comparability, repeated measures ANOVAs will be conducted as secondary analyses to investigate the main effect of time considering all three assessment points. For similar reasons, means and standard deviations (instead of medians and interquartile ranges) will be reported as descriptive data to allow easier comparisons across studies. A further set of ANOVAs will be run to investigate therapist effects. In these secondary analyses, effect size will be expressed by eta squared.

The Reliable Change Index (RCI) will be used to examine the clinical significance of changes on the individual level. Given the uncontrolled nature of the current study's design, a metric will be chosen that considers the tendency of regression to the mean, a threat to the validity of effectiveness studies without a control group. For this reason, the Edwards–Nunnally method will be used to examine the reliability of changes over time (Bauer et al. 2004).

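### The only printed harm question does not name relationships, where the workshop is expected to act, so relationship harm may be under-recorded by an unknown amount

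*Combined protocol and SAP*

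**What the plan says.** Background and aims lists, among the study's aims, "employing active monitoring (not just passive surveillance) of potential iatrogenic effects". Participants and procedure justifies the 4-week assessment by "the focus on changes in perceived quality of interpersonal relationships and related mental health symptoms".

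Measures then describes the harm items: "A couple of freetext questions will also be asked to participants to explore potential iatrogenic effects". One wording is printed, for T2 and T3: "Did you experience any negative change in relation to your mental or physical health during or since the family constellation workshop". An attribution item (yes, no or unsure) follows, on the condition "If respondents answer affirmatively to the second question". No other harm question is printed.

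The same section includes the EXIS.pers, which "will be used to assess the subjective experiences of the individual in their personal social system", with family and friends as examples.

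For the outcome measures the SAP states: "Separate comparisons will be made to explore potential changes from baseline to 4-week post-intervention as well as baseline to 6-month follow-up". It also plans the RCI, by the Edwards–Nunnally method, for change in individuals. It does not list the instruments to which the RCI applies, define a deterioration category, or link the RCI to tolerability. It contains no analysis of the harm items.

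**The concern.** The workshop addresses conflict in the client's personal system, most often the family. Benefit is looked for there, with a dedicated questionnaire. The printed harm question asks about health only. A client whose workshop was followed by a separation or a break with relatives, and who does not think of that as a change in health, can truthfully answer no. The attribution item, which depends on an affirmative answer, may then never be reached.

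At stake is the tolerability result. If harm is asked about less broadly than benefit is measured, the study can report good tolerability partly because it did not ask about the area of life the intervention works on. Harm reports and attributions that were never requested cannot be reliably recovered after follow-up.

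**Working it through.** The documents give no harm rate, sample size or tolerability estimate, so there is no figure of the plan's own to reproduce. The check sets the relevant texts side by side.

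1. **Where the effect is expected.** Participants and procedure names relationship quality and related mental health symptoms as two things. The protocol does not treat a relationship change as the same thing as a mental health change.

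2. **What the printed item covers.** It covers mental or physical health. Relationships are absent. Free text does not widen this, because a client describes only what the opening question has invited.

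3. **What else is asked.** Measures plans more than one question and makes attribution depend on the second. The attribution item asks about the changes, which fits the printed item, so the printed item may well be the second question and the first the one not shown. That reading is likely but not certain. On either reading at least one harm question is unseen, and it may or may not mention relationships.

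4. **Whether the EXIS.pers fills the gap.** It measures the relationship domain and can move in either direction. The Wilcoxon tests and ANOVAs compare groups, so clients who improve can mask a minority who worsen. The RCI works at the individual level and could show that minority, but the SAP does not say that it will be applied to the EXIS.pers or that worsening will be reported as harm. EXIS.pers scores also carry no attribution question.

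5. **Direction and size.** Narrow wording can only remove relationship-harm reports; it cannot add any. Its size can be shown only on assumed figures. Let p be the true proportion of clients with any harm, and s the share of them whose only harm is a relationship harm that no question captures. The recorded proportion is p × (1 − s). Assume p = 10%:
   - s = 0 (all such harm reported as mental health change, or caught by the unprinted question): 10% × 1.0 = 10%, no shortfall.
   - s = 10%: 10% × 0.9 = 9%, a shortfall of 1 percentage point.
   - s = 50%: 10% × 0.5 = 5%, a shortfall of 5 percentage points.

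   Neither p nor s comes from the documents. The lines show how the mechanism works and are not an estimate.

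**The case against.** The strongest reply is that the plan already covers much of this. Every participant is to be asked about harm at both follow-ups, which is active solicitation. A health question matches the stated end results, since Background and aims speaks of mental health and of psychopathological or functional somatic symptoms. A distressing separation may well be reported as a mental health change. The unprinted question may ask about relationships. The EXIS.pers and the RCI supply the means to count clients who worsen, and that count can be added at the analysis stage.

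Most of this stands, and it limits what can be claimed. A reader might infer that relationship harm is not solicited at all, or that the monitoring aim is not met. The documents do not support either inference while one harm question is unseen. A reader might also infer that the reported harm rate can only be too low. That does not follow. The study is uncontrolled and the item counts any negative change during or since the workshop, so unrelated events over six months will be included, and attribution is only the participant's belief. Narrow wording lowers the count and background events raise it; the net direction is not determined.

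What the reply does not remove is that the one visible question leaves out a domain the protocol itself names, and that the SAP does not commit to the analysis that would compensate.

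**Conclusion.** The point holds in a limited form. The printed harm item is narrower than the expected effect, the remaining harm wording cannot be identified, and reliable worsening on the EXIS.pers is not assigned to tolerability. Relationship harm that a client does not regard as a health change may therefore be under-recorded.

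Confidence is high on the gap in wording and low on its size, which the documents do not allow to be estimated. The conclusion assumes that the unprinted question does not ask about relationships and that some clients do not class relationship harm as health. If either assumption fails, little or nothing is lost from the self-reports, and the gap in reporting EXIS.pers deterioration is what remains. The point is worth acting on because the change is small; it does not show that the tolerability result is biased towards safety.

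**What to change.** 1. Print every harm question in Measures and state which one triggers the attribution item.
2. Unless the unprinted question already asks about relationships, extend the item at T2 and T3 to cover *negative change in your mental or physical health, or in your family or other close relationships*. Add a tick-box for the domain (mental, physical, relationship) and ask the existing yes/no/unsure attribution question for each ticked domain.
3. In the SAP, state that the planned RCI will be applied to the EXIS.pers, and that the tolerability results will give the number and percentage of clients with reliable worsening at 4 weeks and at 6 months, with the denominator at each time.

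The cost is a few words in one item, the tick-boxes, and one table from an analysis already planned. The first two changes help only participants not yet assessed; the third can still be made at analysis. The downside is that more relationship changes unrelated to the workshop will be reported. The attribution question separates these only in part, and the EXIS.pers count has no attribution at all, so it should be presented as worsening after the workshop and not as harm caused by it.

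### Harms are collected by ungraded free text plus self-attribution, and the SAP has no harm analysis, so the tolerability result will not reliably separate minor from serious reactions

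*Combined protocol and SAP*

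**What the plan says.** Background and aims (study protocol) includes tolerability in the study's purpose and lists, as its second specific feature, "employing active monitoring (not just passive surveillance) of potential iatrogenic effects".

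The Measures section describes the collection: "A couple of freetext questions will also be asked to participants to explore potential iatrogenic effects". One question is printed, for T2 and T3: "Did you experience any negative change in relation to your mental or physical health during or since the family constellation workshop". If the answer is affirmative, "it will also be asked if they believe the changes are associated with their participation in family constellation therapy (yes, no, or unsure". The text refers to a second question, but only one is printed.

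Participants and procedure sets the timing: a pre-intervention assessment, "a follow-up approximately 4 weeks after the intervention", and a last one "six months post-intervention".

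The Statistical Analysis Plan does not mention iatrogenic effects. It gives no harm endpoint, denominator, coding rule for the free text, or reporting rule. The nearest element is individual-level change: "The Reliable Change Index (RCI) will be used to examine the clinical significance of changes on the individual level". It explains the choice of RCI method with "Given the uncontrolled nature of the current study's design".

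**The concern.** A tolerability statement is useful only if it can distinguish a passing low mood from a reaction that disrupted someone's life or led them to seek care. The described items ask whether something negative happened and whether the client links it to the workshop. They do not ask how bad it was. Free text allows a respondent to say so but does not prompt it, and the SAP has no rule for turning what is written into a severity category.

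At stake is the reading of the harm result. A moderate share of affirmative answers could be presented as harmless or as alarming from the same data. Any severity classification would have to be devised after the answers had been seen, and only for those who chose to elaborate.

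**Working it through.** The documents contain no harm rate, sample size or threshold, so there is no planned figure to reproduce. The check is a comparison of sections, followed by a labelled illustration.

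**Step 1: aim against measurement**

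| Needed to describe tolerability | Where the plan covers it |
|---|---|
| Occurrence of a negative change | Measures, T2 and T3 |
| Client's view of cause | Measures, three categories, after an affirmative answer |
| Severity or interference with daily life | No prompt described; available only if volunteered in free text |
| Care sought | No prompt described; available only if volunteered |
| Coding of the free text | Not in Measures or SAP |
| Harm summary and denominator | Not in SAP |
| Background rate | None: no control group |

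**Step 2: what the RCI adds**

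The RCI compares a person's score at one assessment with the score at another. On scales such as the BSI and PHQ-15 it could show lasting worsening at about 4 weeks or at 6 months. Two limits follow from the schedule and the SAP text:
- A reaction that began after the workshop and resolved before the 4-week assessment, or that arose and resolved between 4 weeks and 6 months, need not appear in the scores.
- The SAP does not name the scales to which the RCI will be applied, does not say that deterioration will be reported, and does not link the RCI to harms.

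**Step 3: how much the missing grading could matter**

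Let *n* respondents include *s* whose free text shows a serious change and *u* who report a change but give too little detail to classify. The observed serious-harm share then lies between

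*s*/*n* and (*s* + *u*)/*n*.

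The width is *u*/*n*. It vanishes if everyone describes severity and is widest if nobody does. The documents give no basis for predicting *u*.

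Illustration only (assumed: *n* = 100, 10 affirmative answers, none classifiable, so *s* = 0 and *u* = 10): the share lies between 0/100 = 0% and 10/100 = 10%. Sampling error comes on top of that. The exact (Clopper–Pearson) 95% limits for *x* of *n* are the 2.5% quantile of Beta(*x*, *n* − *x* + 1) and the 97.5% quantile of Beta(*x* + 1, *n* − *x*):

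| Serious cases | Share | Exact 95% interval |
|---|---|---|
| 0 of 100 | 0% | 0 to 3.6% |
| 1 of 100 | 1% | 0.03 to 5.4% |
| 10 of 100 | 10% | 4.9 to 17.6% |

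For the first row, the upper limit is 1 − 0.025^(1/100) = 3.6%. With grading, the study would report one of these rows. Without it, and with no usable free text, the same ten answers fit all three.

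**The case against.** The strongest reply has four parts.

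- **The questions are free text.** A reader might infer that the study records only a yes or no plus attribution. The Measures section does not support that: respondents can write what happened, and some will. This stands. What remains is that the detail is neither prompted nor covered by a coding rule.
- **Worsening is measured elsewhere.** The scales are given before and after the workshop, and the RCI method was chosen with regression to the mean in mind. This stands for lasting deterioration, within the limits in Step 2. It is a reason to use the RCI for harms, which the SAP does not yet do.
- **The aim is modest.** A reader might infer that the tolerability aim cannot be answered at all. That goes too far. Asking directly about harm at both follow-ups is active monitoring, the questions are framed as exploratory, and no serious-harm rate is promised. Nor does the SAP plan a bare count; it is silent. The full item set is also not printed, so the point rests on what is described.
- **Background change.** A reader might infer that the harm item should also have been asked at baseline. Its wording is tied to the workshop, so it could not be. A look-back over earlier months would be a different question, and its rate could not be subtracted, because people may book when they are doing badly. The absence of a comparator is a limit to state; a baseline item would not cure it.

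**Conclusion.** The point holds as a shortfall in harm measurement and analysis. As described, severity will be known only for respondents who volunteer it, nothing in the SAP says how it will be classified or reported, and the RCI is not directed at harms and would miss transient reactions. The tolerability result will therefore not reliably separate minor from serious reactions.

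The size cannot be fixed from the documents. The uncertainty about the observed serious-harm share equals the proportion of respondents with an unclassifiable negative change. In the assumed example it reaches ten percentage points, the extreme case in which no free text is usable.

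The conclusion assumes that the question not printed does not itself ask about severity or care sought. If it does, the Measures part of the point falls away and the SAP part remains. The matter is worth correcting because harm monitoring is a stated aim and the remedy is cheap; it does not affect the effectiveness analyses.

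**What to change.** **Measures.** Keep the free text. After each 'yes' at T2 and T3, add two closed items:
1. interference with daily life (none / slight / moderate / severe);
2. professional help sought because of the change (yes / no).

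Print all the harm questions, including the one now only referred to.

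**SAP.** Add a short harm section with one table that reports:
- the share with any negative change and the share with moderate or severe change, by attribution category (yes / unsure / no), each with an exact 95% interval;
- the share with reliable deterioration on the BSI and the PHQ-15, from the RCI already planned.

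Give T2 and T3 separately, with the respondents at each assessment as denominator. The T3 question reaches back to the workshop, so one event may be reported at both times. State that, without a control group, these rates cannot be separated from background change.

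The interference levels and the moderate-or-severe cut are one workable choice; what matters is that they are fixed before the answers are read.

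**Cost.** Two short items for those who report a negative change, and one table. No additional visit or staff.
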